#### **Statistical analysis:**

Statistical package for the social science (SPSS) version 21(SPSS®, IL) computer software will be used for descriptive and inferential statistics in all parameters. Descriptive statistics will be presented for each clinical parameter. Primary hypothesis will be analyzed if it is normally distributed. ANCOVA procedure will be used to test the relation between the primary variables and control the influences of the covariates. Statistical significance is denoted when P < .05.

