#### **Biopsy Procedure:**

- After 8 months of healing, a full-thickness flap will be reflected and previous antrostomy site will be located using the same surgical template. Two trephines (2.75mm internal diameter and 3.5mm external diameter, ACE Surgical Supply Company, Inc., Brockton, MA) will be used to collect at least 8mm length biopsy specimen. Two cores will be taken from each patient site; one core from the previous lateral window of each sinus augmentation site without interfering with implant placement and one core from the implant osteotomy site. When obtaining the core from the implant osteotomy site, at least 8mm in length of the grafted bone will be included in the core. The trephines are marked at 8mm,10mm,13mm,15mm. The core samples will be kept in the trephine in 10% buffered formalin, coded and mailed to the laboratory for the histomorphometric analysis.
- 2. The alveolar ridge will be prepared for implant placement, in accordance with the conventional surgical protocol, and implants of appropriate dimensions will be placed.

Immediately after insertion the stability of the implants will be recorded by measuring the ISQ values.

- 3. Post-operative care instructions will be provided as described previously.
- 4. Appropriate healing time for the implants will be allowed for osseointegration, and definitive restorative prostheses will be constructed accordingly.

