#### Histomorphometric analysis:

All the specimens will be digitized at the same magnification using a NIKON ECLIPSE 50i microscope (Nikon corporation, JAPAN) and a SPOT INSIGHT 2 mega sample digital camera (Diagnostic instruments Inc, USA). Histomorphometric measurements will be completed using a combination of SPOT 5.1 Advanced Software (Diagnostic instruments Inc, USA) and Adobe Photoshop (Adobe Systems, Inc.).

The measurements to be obtained and presented in tabular form are:

- 1. Percentage of the area of the core, which is bone. Of the bone, the percentage of vital and non-vital bone will be determined.
- 2. Percentage of non-bone material. (ABBM)
- 3. Percentage of connective tissue.

The histomorphometric data for each specimen will be recorded as the average of the 2 slides from the specimen.

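### Tests on all parameters at an unadjusted .05, with no single new-bone variable named, leave the error rate for the new-bone hypothesis at about 10% or more unless one measure and one core rule are fixed in advance

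*Combined protocol and SAP*

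**What the plan says.** The Objective and Null Hypothesis sections name one target, new bone formation compared between the two graft materials. The Statistical analysis section also has a single hypothesis in view: "Primary hypothesis will be analyzed if it is normally distributed".

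The same section then says that the software "will be used for descriptive and inferential statistics in all parameters", and that the "ANCOVA procedure will be used to test the relation between the primary variables and control the influences of the covariates". It names neither the primary variables nor the covariates. Its only error-rate statement is "Statistical significance is denoted when P < .05". It gives no ranking, testing order, multiplicity adjustment or sidedness.

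The Histomorphometric analysis section lists what will be tabulated. The first item is "Percentage of the area of the core, which is bone", with the vital and non-vital shares of that bone. The others are residual graft (ABBM) and connective tissue. The two slides of a specimen are averaged. Under Biopsy Procedure, "Two cores will be taken from each patient site", one at the former lateral window and one at the implant osteotomy. No rule says how the two cores give one value for a sinus.

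**The concern.** A single hypothesis tested once at .05 has a 5% chance of a false positive. Here the hypothesis is single but its variable is not. Three quantities could reasonably be called new bone, each available from two cores or their average. If more than one is tested and any P below .05 counts, the hypothesis is rejected too often when the materials do not differ. If one is chosen after the results are seen, the effect is the same.

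At stake is a claim that one graft material forms more bone than the other, resting on whichever bone measure crossed the threshold. A second, lesser matter is that a difference in ABBM or connective tissue could be reported as significant with no indication of how many tests were made.

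**Working it through.** The plan states no power, effect size, SD or family-wise error rate, so there is no figure of its own to reproduce beyond the .05 threshold.

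**Inputs from the documents**
- 10 sinuses per group, two cores per site, slides averaged within a specimen.
- Four distinct listed measures: bone %, vital share of bone, ABBM %, connective tissue %. The non-vital share is 100 minus the vital share and adds no test.
- A third bone measure follows from the first two: vital bone % of core = bone % × vital share / 100.

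**Assumed inputs**
- Bone 25% and ABBM 30%, SD 8 points each, uncorrelated. Connective tissue is 100 − bone − ABBM.
- Vital share 85%, SD 8, independent of bone %.
- Correlation between the two cores of a sinus 0.3, 0.5 or 0.7.
- All 20 sinuses independent. Bilateral cases are a separate question.
- Two-sided t tests. The plan names ANCOVA, but with unnamed covariates it cannot be simulated. A valid ANCOVA also has a 5% level per test.

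**Reference values for independent tests**

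P(at least one P < .05) = 1 − 0.95^k
- k = 2: 1 − 0.9025 = 9.75%
- k = 4: 1 − 0.8145 = 18.5%
- k = 8: 1 − 0.6634 = 33.7%

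The tissue percentages are dependent, so simulation is needed. With 40,000 null trials per setting, the Monte Carlo standard error is at most about √(0.29 × 0.71 / 40,000) = 0.2 points. The range in each cell is over the three between-core correlations.

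| Measures tested | On core averages | Each core site separately |
|---|---|---|
| Bone % alone | 4.8% to 5.1% | 8.5% to 9.6% |
| Bone % and vital share | 9.6% to 10.0% | 16.4% to 18.2% |
| Those two and vital bone % of core | 10.7% to 11.2% | 18.2% to 20.2% |
| All four listed measures | 15.8% to 16.4% | 26.3% to 28.8% |

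The first three rows bear on the new-bone hypothesis. The last row is the chance that some tissue percentage is falsely called significant.

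**Sensitivity.** Correlation between bone and ABBM matters only for the last row. Varying it from −0.8 to 0.3, and the between-core correlation from 0 to 0.8, gives about 15% to 17% for four measures with one value per sinus, and 23% to 31% for four measures in two cores.

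**After the fix.** One named measure with one value per sinus returns to 5%, as in the first row, left column.

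**The case against.** The strongest reply is that the trial already has one hypothesis. ABBM and connective tissue cannot reject a null about new bone, so the 16% and 26% to 29% figures do not measure its error rate. That stands. A reader might infer that any significant tissue percentage would count against the null, and the Null Hypothesis section does not support this.

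Three further points have force:
- The plural in primary variables does not prove that there are several primary outcomes. A relation needs two variables, and graft material with bone percentage would satisfy the wording.
- That each listed percentage will be tested is an inference from the reference to all parameters. The Histomorphometric analysis section promises only measurement and tabulation.
- Nothing says the core sites will be tested separately. The right-hand column shows what the silence permits; it is not a stated plan.

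It can also be said that .05 is a per-test threshold, that no family-wise rate is claimed, and that this is a pilot. The pilot label lowers the consequences. It does not settle the matter, because the plan sets a formal null and a significance threshold without saying which bone measure the threshold applies to. Even with everything except bone set aside, two bone measures roughly double the error.

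**Conclusion.** The point holds for the new-bone hypothesis. With inferential tests on all parameters at an unadjusted .05 and no named bone variable, the chance of a false positive is about 10% to 11% for two or three bone measures on core averages. It is about 16% to 20% if the core sites are tested separately. It is 5% only if one measure and one core rule are fixed in advance.

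The chance of any false significant tissue percentage is about 16% for four measures on core averages and about 26% to 29% by site. These last figures should not be quoted as the error rate of the trial's hypothesis.

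All figures rest on assumed SDs and correlations and on the number of tests actually run, none of which the documents give. The choice between histology and microCT is also left open; it and ISQ are not counted here. The sponsor should make the change, although the pilot status limits the consequences.

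**What to change.** In the Statistical analysis section, before unblinding:
- Name one primary variable, for example vital bone as a percentage of section area, taken as the pre-specified mean of the two cores of each sinus. State which measurement method supplies it.
- State how osteoid is classified. The section on non-decalcified processing gives it the same stain colour as non-vital bone, so the vital/non-vital split may not match newly formed bone.
- Test only that variable, at two-sided .05.
- Label total bone, vital share, ABBM, connective tissue, per-site results and ISQ as secondary or exploratory, and report them as estimates with 95% confidence intervals.

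If more than one confirmatory test is wanted, Holm or Bonferroni would serve. Bonferroni over the four measures in one core (.05 / 4 = .0125 each) gave a simulated error of 4.6%.

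The change needs no extra patient, specimen or procedure. Its costs are that secondary percentages can no longer support a confirmatory claim, and that the Adherence to Protocol section requires a written amendment agreed by the sponsor and approved by the Institutional Review Board.

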#### **Adherence to Protocol:**

Departure from the protocol will not be permitted except for medical conditions that require management not specified in the protocol. Changes in the protocol may be made only by written amendment agreed upon by the sponsor and subsequently approved by the Institutional Review Board.

#### Patient Withdrawal and/or Replacement:

If a subject decides to withdraw from the study prior to sinus augmentation, this individual will be replaced with another subject. If a perforation of the sinus membrane (> 5 mm) occurs during the surgical procedure, the site will be closed and the augmentation procedure will be aborted. This individual will be replaced with another subject.

If a subject is withdrawn from the study following sinus augmentation, all data associated with this individual will be reported but not included in the final results and analysis. If the subject is unable to attend the required post-operative sessions or is uncooperative, this individual may be dismissed from the study.

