#### **Pre-operative procedure**

- At a pre-surgical appointment, the patient's vital signs (blood pressure, pulse rate) will be recorded and the patient's medical history will be updated. At this point, patients will be randomly assigned to Group A or B.
- 2. Patients will be given the following three choices of anesthesia for the sinus surgery:
  - a) Local anesthesia (LA) only.
  - b) LA in conjunction with oral sedation (Halcion 0.25mg, Roxane Laboratories Inc., Columbus, OH). Administered 30 minutes before the appointment.

c) LA in conjunction with intravenous (IV) sedation.

A patient who chooses IV sedation will have a pre-surgical interview with the anesthesiologist (Surgery Center for Dentistry, Loma Linda University School of Dentistry) who will conduct sedation at the time of the surgery.

- 3. All patients will be questioned regarding drug allergy and prescribed with appropriate antibiotics (Amoxicillin 500 mg or Clindamycin 300mg, TID for 10 days, to start day 1 before the day of surgery) analgesic (Ibuprofen 800 mg) to take 1 tab 1 hour before the surgery and for post-operative usage as needed for pain. The patient will also be instructed to rinse with 0.12% chlorhexidine gluconate solution (Peridex, Zila Pharmaceuticals Inc., Phoenix, AZ) twice a day starting 1 week before the surgery to continue for 2 weeks after the surgery.
- 4. The radiographic template will be converted into a surgical template. The proposed implant locations in the radiographic template will be finalized and modified if necessary after reviewing the CBCT scan with the template in place. The location of the anterior wall of the sinus cavity will be marked on the surgical template.
- 5. All pre-operative and postoperative instructions will be given to the patient in an oral and written format. All of the patient's questions about the instructions will be answered.

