#### **Post-operative instructions**

All patients will be instructed to maintain a liquid diet for 2 weeks after the sinus surgery, continue on a soft diet for one month and general diet for the remaining duration of the healing phase. If a patient presents with a removable prosthesis, the prosthesis will be evaluated for proper tissue adaptation. If the tissue adaptation is poor, the prosthesis will be relined using a soft reline material (GC Reline Soft, GC, Alsip, IL) following the surgery. The patient will be advised to avoid nose blowing and placing any undue pressure on the surgical site. The patient will be instructed to rinse gently with 0.12% chlorhexidine gluconate solution (Peridex) for the first two weeks following the surgery. Recall examinations will be scheduled two weeks following the surgery for suture removal and at 1, 3, and 6 months after sinus augmentation and 2 weeks before biopsy and implant placement. The biopsy and implant placement procedure will be performed 8 months after the grafting procedure. A CBCT scan will be taken 2 weeks before implant placement to determine the final implant position and size. (The post operative CBCT scan after sinus augmentation and prior to implant placement is standard protocol )

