#### Histology / MicroCT assessment

The trephine with the retrieved specimens will be placed in 10% neutral buffered formalin. Each specimen will be labeled and packaged in an individual container, which will then be numerically coded to keep the patient's information confidential and examiners will be blinded. Specimens (40) will be sent to the Hard Tissue Research Laboratory, University of Minnesota School of Dentistry for histomorphometric analysis. Or the specimens will be analysed by using a MicroCT at the university of Loma Linda, center for radiation research. The microCT will give us digital reconstruction of the 3D structure of the core material. This will be analysed for new bone formation, amount of graft material remaining, interaction between the graft and the patient's native bone.

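### Data from subjects withdrawn after grafting are left out of the test and dismissal is discretionary, so some obtainable 8-month outcomes can be lost after assignment

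*Combined protocol and SAP*

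**What the plan says.** Assignment is made at the pre-surgical appointment: "At this point, patients will be randomly assigned to Group A or B" (Pre-operative procedure). The section headed Informed Consent, which also covers randomisation, plans 10 sinus augmentations per group and treats each sinus of a bilateral patient as its own randomisation unit.

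After grafting, recalls take place at two weeks for suture removal, then "at 1, 3, and 6 months after sinus augmentation and 2 weeks before biopsy and implant placement" (Post-operative instructions). "The biopsy and implant placement procedure will be performed 8 months after the grafting procedure" (same section). Under Biopsy Procedure, "Two cores will be taken from each patient site". Under Histology / MicroCT assessment, "Specimens (40) will be sent to the Hard Tissue Research Laboratory". The only mention of blinding concerns the coded specimen containers ("information confidential and examiners will be blinded").

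Patient Withdrawal and/or Replacement treats losses in three ways:

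- Subjects who withdraw before grafting, or whose procedure is aborted for a perforation above 5 mm, are replaced.
- For a subject withdrawn after grafting, "all data associated with this individual will be reported but not included in the final results and analysis". No replacement is stated.
- "If the subject is unable to attend the required post-operative sessions or is uncooperative, this individual may be dismissed from the study". No threshold or decision-maker is given.

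Statistical analysis names ANCOVA and a significance level of .05. It defines no analysis set and no handling of missing outcomes.

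**The concern.** Withdrawal and dismissal both happen after assignment. A rule that removes those subjects from the test, whether or not their outcome exists or could be obtained, means the tested groups need not be the groups as assigned. Dismissal adds discretion. It is optional, its grounds are broad, and nothing says that whoever decides is unaware of the graft used.

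If losses are unrelated to outcome, the cost is a wider confidence interval. If they are related to outcome and unequal between the arms, the estimated difference in new bone moves in a direction that cannot be predicted from the documents. With 10 sinuses per arm, one lost sinus is 10% of an arm.

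**Working it through.** **1. Which losses the rule causes.** Histomorphometric values come only from the cores (Biopsy Procedure; Histomorphometric analysis). The recalls at two weeks and at 1, 3 and 6 months supply none. There are three situations:

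- Subject leaves before biopsy and never returns: no outcome exists, and no analysis rule can recover it.
- Subject misses recalls but would still come for the 8-month surgery: the outcome is obtainable, but dismissal can forgo it.
- Subject is withdrawn after biopsy: the outcome exists, and the rule sets it aside. This is a narrow case, because the protocol gives no dated study visit after biopsy.

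Only the second and third are avoidable.

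**2. The plan's own count.** 20 sinuses x 2 cores = 40 specimens, which matches the stated figure and leaves no room for loss. Each lost sinus removes 2/40 = 5% of the cores.

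**3. Inputs for size.** From the documents: 10 sinuses per arm and alpha .05, taken as two-sided because the null hypothesis is one of no difference. Assumed, because the documents give no withdrawal rate or SD: 1 or 2 sinuses lost from one arm only; normal outcome in SD units; independent sinuses; loss driven by a score with correlation r to the outcome.

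**4. Precision if loss is unrelated to outcome.** The 95% CI half-width in SD is t(0.975, n1+n2-2) x sqrt(1/n1 + 1/n2):

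- 10 v 10: 2.101 x 0.447 = 0.94
- 9 v 10: 2.110 x 0.459 = 0.97
- 8 v 10: 2.120 x 0.474 = 1.01

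**5. Shift if loss is related to outcome.** For 10 standard normal values the expected lowest is -1.539 and the second lowest -1.001. Losing exactly those values raises the arm mean by 1.539/9 = 0.171 SD (one lost) or (1.539 + 1.001)/8 = 0.318 SD (two lost). For correlation r, multiply by r. The rejection rate of a true null is from 400,000 simulated trials per cell, using an unadjusted pooled t test as a simplification of the planned ANCOVA.

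| r | Shift, 1 lost | Shift, 2 lost | Rejection, 1 lost | Rejection, 2 lost |
|---|---|---|---|---|
| 0 | 0 | 0 | about 5% | about 5% |
| 0.3 | 0.05 SD | 0.10 SD | 5.2% | 5.5% |
| 0.5 | 0.09 SD | 0.16 SD | 5.5% | 6.4% |
| 1 (upper bound) | 0.17 SD | 0.32 SD | 7.5% | 11.6% |

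With the same loss in both arms, the difference does not shift.

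**6. Subject versus sinus.** Withdrawal is by subject, while randomisation can be by sinus. One bilateral patient could remove one sinus from each arm or two from the same arm. The first gives 9 v 9, with half-width 2.120 x 0.471 = 1.00 SD. The second gives 8 v 10, so one withdrawal is enough to produce the two-lost column. That column treats the two sinuses as independent, which sinuses from one patient need not be.

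**7. What a change of rule can recover.** In the upper-bound case with two lost, suppose one sinus is recovered. The shift falls from 0.318 to 1.539/9 = 0.171 SD or 1.001/9 = 0.111 SD, so 46% or 65% is removed. At r = 0.5 the same step takes 0.16 SD to about 0.09 or 0.06 SD. If neither sinus can be biopsied, nothing is recovered.

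**The case against.** The strongest objection is that the rule hardly touches the tested outcome. A subject gone before 8 months has no value to analyse under any rule, and little follows biopsy that could prompt a withdrawal. The dismissal route needs three things together: the option is used, dismissal counts as withdrawal, and the subject would still have come for surgery. The documents give no frequency for any of these and do not say outright that dismissed subjects count as withdrawn. All of this stands, and it limits the concern to sinuses that were or could be biopsied. If dismissal is not withdrawal, however, no rule at all covers the data of dismissed subjects, and that also needs wording.

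A reader might infer that the rule biases the trial, or that its error rate is 11.6%. The documents do not support that. The upper bound needs the two lowest values to be lost from one arm. No histology exists when a subject is dismissed before biopsy, so nobody can select on the measured outcome. At r = 0.3 the shift is only about 5% to 9% of the CI half-width (0.051/0.969 and 0.095/1.006).

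A reader might also infer that a revised analysis set restores the randomised groups. It does not. Sinuses without cores stay missing, and subjects replaced after assignment but before a completed graft stay outside.

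Finally, this is a pilot and the excluded data are still to be reported. That makes the losses visible and lowers the priority, but the protocol also states a null hypothesis and a significance test, and reporting does not change what is tested.

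**Conclusion.** The concern holds in a limited form. The exclusion is an explicit rule, and nothing elsewhere in the document offsets it. That part is certain. A material effect is not: bias is possible, unproven and of unknown direction.

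Under the assumed loss of 1 or 2 of 10 sinuses from one arm, with r of 0.3 to 0.5, the shift is about 0.05 to 0.16 SD with rejection of about 5.2% to 6.4%. The figures of 0.17 to 0.32 SD and 7.5% to 11.6% are upper bounds only. Loss unrelated to outcome widens the half-width from 0.94 to 0.97 or 1.01 SD and causes no bias. These results depend on the assumed losses and correlations, on independent sinuses and on an unadjusted test. Priority is minor to moderate.

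**What to change.** In Patient Withdrawal and/or Replacement, keep the commitment that all data on withdrawn subjects are reported. Replace the clause that keeps those data out of the results and analysis with wording such as:

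*Every grafted sinus with evaluable cores is analysed in its assigned group, regardless of recall attendance, dismissal or later withdrawal, unless consent for data use is withdrawn. Grafted sinuses without cores, and post-assignment replacements, are tabulated by arm and reason, with their recorded complications.*

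After the dismissal sentence, state that missed recalls alone do not remove a subject from outcome collection where the subject remains willing and proceeds to the already planned biopsy and implant surgery. Have the table identify bilateral patients, so that one withdrawal affecting two sinuses can be seen. Name the same set in Statistical analysis. Leave all clinical management rules unchanged.

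The result is an as-assigned set of sinuses with cores. It does not remove bias from sinuses that never yield cores or from pre-graft replacements; the table only makes those visible.

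The cost is a short written amendment, by the route in Adherence to Protocol, and one extra table. No visits or subjects are added and the planned 40 specimens are unchanged. A subject who would otherwise have been dismissed would still be asked for the planned cores, one of which is taken apart from the implant site, so continued willingness has to be a stated condition.

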#### **Informed Consent:**

In accordance with the standards of conduct established by the Institutional Review Board of Loma Linda University, participants will be required to sign an informed consent. The purpose and the nature of the study will be explained to the subjects by one investigator (SU) and patient who will meet our inclusion criteria will then be invited to participate. Subjects will be required to read, understand, and sign the consent form before being enrolled in the study. Hard copy will be retained following the standard protocol set by the Institutional Review Board of Loma Linda University. Randomization – Quickcalcs software from Graphpad (Graphpad software Inc, La Jolla, CA USA) will be used to randomly assign patients. All patients will undergo sinus augmentation and will be randomly placed into two groups according to the graft material to be used in the surgical procedure. If a patient requires bilateral sinus augmentation, (two sinus on either side in the same patient) each sinus will be considered as one unit for the randomization procedure.

Group A: 10 Maxillary sinus augmentation using ABBM (InterOss).

Group B: 10 Maxillary sinus augmentation using ABBM (Bio-Oss).

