#### Surgical and post-operative complications

Surgical and post-operative complications such as perforation of the sinus membrane, acute or chronic sinus infection (pain, suppuration, swelling, nasal fluid leakage), bleeding, wound dehiscence, and exposure of the graft will be recorded.

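### Excluding all data from patients withdrawn after grafting leaves the final complication summary covering only those who stayed

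*Combined protocol and SAP*

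**What the plan says.** The section on patient withdrawal and replacement sets the rule. It applies "If a subject is withdrawn from the study following sinus augmentation", whatever the reason, and its effect is that "all data associated with this individual will be reported but not included in the final results and analysis". The same section adds a discretionary route out: "If the subject is unable to attend the required post-operative sessions or is uncooperative, this individual may be dismissed from the study". Replacement is provided for withdrawal before augmentation and for a membrane perforation above 5 mm, but not for withdrawal after grafting.

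The section on surgical and post-operative complications says that events including "acute or chronic sinus infection (pain, suppuration, swelling, nasal fluid leakage), bleeding, wound dehiscence, and exposure of the graft will be recorded". It names no analysis set, denominator or comparison. The post-operative instructions fix when events can be picked up: "Recall examinations will be scheduled two weeks following the surgery for suture removal and at 1, 3, and 6 months after sinus augmentation", with a further visit 2 weeks before the biopsy at 8 months.

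The statistical analysis section promises that "Descriptive statistics will be presented for each clinical parameter" and defines no safety population. Under the randomization text in the informed consent section, when a patient needs both sides treated, "each sinus will be considered as one unit for the randomization procedure".

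**The concern.** One rule is serving two purposes and suits only one of them. A patient who leaves before the 8-month biopsy has no core, so leaving that patient out of the histomorphometric comparison is natural. An infection or graft exposure already recorded at a recall visit is a complete observation, and the missing biopsy is no reason to set it aside. As written, the rule covers all of the patient's data and so sets aside both.

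The plan defines no complication rate by material. But the introduction says the study will compare clinical performance as well as histomorphometry, and the complications section is where post-graft harm is collected. If complications are described in the final results, the description covers only sinuses of patients who stayed. If a complication makes leaving or dismissal more likely, the figure for that material is too low, and a reader has to add back events reported elsewhere.

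There is also a mismatch of units. The rule removes an individual, whereas the sinus is what is randomised. Withdrawing one bilateral patient removes two sinuses, either both from one group or one from each, so an event with one material can change the other material's denominator.

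**Working it through.** The plan states no complication rate, withdrawal rate or complication analysis, so there is no figure to reproduce. The check has a textual part and an arithmetic illustration.

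**Text.**

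1. The exclusion covers all data of the individual, so it includes complications.
2. It is triggered by any withdrawal after grafting. Eight months pass between grafting and biopsy, with recalls at 2 weeks and 1, 3 and 6 months, so an event can be on record before the patient leaves.
3. The rule contrasts reporting with inclusion in the final results. No section says where or how the reporting is done, or that it is by material.
4. No section provides for a complication summary over all grafted sinuses.

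**Inputs.** The randomization text gives 10 sinuses per group. Every event count and probability below is an assumption.

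**Single-group illustrations.** The rate shown is events among stayers divided by sinuses of stayers. The full rate is all events divided by 10. Intervals are exact (Clopper-Pearson) 95%.

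| Assumed case | Over all grafted sinuses | Under the rule |
|---|---|---|
| (a) 3 events, nobody leaves | 3/10 = 30% (6.7 to 65.2%) | 3/10 = 30% (6.7 to 65.2%) |
| (b) 3 events, one affected unilateral patient leaves | 3/10 = 30% (6.7 to 65.2%) | 2/9 = 22.2% (2.8 to 60.0%) |
| (c) 1 event, that unilateral patient leaves | 1/10 = 10% (0.25 to 44.5%) | 0/9 = 0% (0 to 33.6%) |
| (d) 1 event, an unaffected unilateral patient leaves | 1/10 = 10% (0.25 to 44.5%) | 1/9 = 11.1% (0.3 to 48.2%) |

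**Bilateral illustration (e).** Assume one event per group, so 1/10 v 1/10, with the InterOss event in a bilateral patient who withdraws.

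- Other sinus unaffected and grafted with Bio-Oss: InterOss 0/9 (0%) v Bio-Oss 1/9 (11.1%).
- Both sinuses grafted with InterOss: 0/8 (0%; 0 to 36.9%) v 1/10 (10%).

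**Expected rate shown.** Let p be the true risk per sinus, q the probability of withdrawal after a complication and r the probability without one, treating each sinus as one patient:

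rate shown = p(1 − q) / [p(1 − q) + (1 − p)(1 − r)]

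With p = 0.20 and r = 0:

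- q = 0: 0.20 / (0.20 + 0.80) = 20.0%
- q = 0.25: 0.15 / (0.15 + 0.80) = 15.8%
- q = 0.50: 0.10 / (0.10 + 0.80) = 11.1%
- q = 1: 0 / 0.80 = 0%

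With p = 0.10 and r = 0, the same values of q give 10.0%, 7.7%, 5.3% and 0%.

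When q = r the rate is unchanged. For example, p = 0.20 with q = r = 0.1 gives 0.18 / (0.18 + 0.72) = 20.0%. The understatement therefore depends on q exceeding r.

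**The case against.** The strongest reply is that nothing is hidden. The sentence that excludes a withdrawn patient's data also requires them to be reported, and with about 20 sinuses a reader could add the events back. This stands as far as it goes: there is no suppression. But the plan does not say in what form, or by which material, the data would be reported, and the summary in the final results would still be the incomplete one.

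Second, the objective and null hypothesis concern new bone formation only, and no complication rate is planned. On that footing the final results could be read as the histomorphometric results alone. It is true that no rate is planned. The narrow reading, however, conflicts with a rule that expressly covers all of the individual's data.

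Third, no section links a complication to withdrawal or dismissal. The stated grounds for dismissal are non-attendance and non-cooperation, and the protocol-adherence section allows departures for medical conditions needing management the protocol does not specify. This stands in full: the direction and size of any bias are conditional, and case (d) moves the rate upward.

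Fourth, the counts are invented, the q = 1 row is an extreme, and the intervals overlap widely. This also stands, and no between-group conclusion is claimed to change.

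Finally, the plan's 20 patients, 20 sinuses and 40 specimens (two cores per site) leave no room for bilateral patients, so illustration (e) needs fewer than 20 patients. The tension is real but minor, because the randomization text expressly allows for bilateral patients.

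**Conclusion.** The concern holds. Followed as written, the rule leaves any complication summary in the final results covering only the sinuses of patients who stayed. That follows from the wording and needs no assumption about rates.

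Whether the summary is also biased depends on whether affected patients leave more often than unaffected ones, which the documents do not say. If they do, harm is understated. With 10 sinuses per group, one such withdrawal can turn 10% into 0% or 30% into 22%. At a true risk of 20% with no other withdrawals, the expected figure falls to 15.8% if a quarter of affected patients leave and to 11.1% if half do. If leaving is unrelated to complications there is no systematic error, only a denominator that is not the number grafted.

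The effect is on the reported figure for each material. It does not reach the bone-formation test or any between-group inference. The change should be made because it is cheap and the rule is explicit, not because the bias is known to be large.

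**What to change.** In the section on patient withdrawal and replacement, limit the exclusion to the histomorphometric analysis. In that section and in the statistical analysis section, state three things:

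- Post-operative complications are summarised by graft material over every sinus that received graft, including those of patients later withdrawn or dismissed.
- Events are counted up to last contact.
- The denominator shown is the number of sinuses grafted with each material.

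This is one or two sentences and uses data already being recorded, with no extra patients, visits or staff. Under the protocol-adherence section it needs a written amendment with Institutional Review Board approval, so it should be made in advance. The downsides are that complication rates may look less favourable and that follow-up is shorter for withdrawn patients, which the report should state.
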